6.3 Changes to Planned Analysis according to SAP Version 1.0

The original planned analysis, definition and scope of outputs will remain in the version 2.0 of SAP. The changes to the planned analysis is described in Appendix 4 List of Abbreviated Scope Based on SAP Version 2.0 which contains the planned outputs. The N=1200 subjects will not be enrolled, instead the analysis is based on the N=129 enrolled at the time of the decision to pause the study.

6.4 Changes to Protocol from Version 2.0 to Protocol Amendment #1

- For this study an abbreviated CSR will be produced due to the reduced sample size. The CSR will be based on the reduced scope (see Appendix 4 List of Abbreviated Scope Based on SAP Version 2.0). For the primary safety endpoints, key analysis will be included related to summary/occurrence of solicited adverse events, duration of solicited adverse events, unsolicited adverse events, adverse events of special interest and adverse events leading to either study or vaccine withdrawal.
- The analysis of number and percentage of subjects with Grade 3 adverse reactions or SAE considered related to the trial vaccine according to the investigator with 95% credibility intervals on the beta (0.5, 1.5) prior distribution and estimate will not be performed due to the small number of subjects.
- For the secondary immunogenicity endpoints, the immunogenicity set was planned for Day 1 (baseline), Day 29, Day 120, Day 211 and Day 393. Instead, the analysis will be performed with per protocol immunogenicity set for all available time points (Day 1(baseline), Day 29, Day 43 and Day 120).
- Exploratory endpoints related to CMI response: these analyses will not be finalized due to invalid samples and small sample size.
- Exploratory endpoints related to occurrence of confirmed COVID-19 cases: analysis will not be performed.
- Only time points up to Day 120 will be included.

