**Table 4 Estimate of Number of Subjects Seroconverting for SARS-CoV-2 S Protein Antibodies and 95% Credibility Interval**

Rate (%)	Sample Size			
	150		1200	
	N	95% CI	N	95% CI
80	120	80.2 (73.5 - 86.1)	960	80 (77.7 - 82.2)
85	128	85.5 (79.5 - 90.6)	1020	85 (82.9 - 87)
90	135	90.1 (84.9 - 94.3)	1080	90 (88.3 - 91.6)
95	142	94.7 (90.6 - 97.6)	1140	95 (93.7 - 96.2)
100	150	99.9 (99.4 - 100)	1200	100 (99.9 - 100)

CI: credibility interval; N: subjects seroconverting for SARS-CoV-2 S protein antibodies

Table 5 provides probabilities (in %) that the following 2 conditions are simultaneously met for assumed true adverse reaction rates and for assumed true rates of subjects seroconverting for SARS-CoV-2 S protein antibodies and for different sample sizes:

- There is a  $\geq 80\%$  probability that the true rate of Grade 3 adverse reactions is  $\leq 33\%$ , and
- There is a  $\geq 90\%$  probability that the true rate of subjects seroconverting for SARS-CoV-2 S protein antibodies is  $> 95\%$ .

For example, assuming a true adverse reaction rate of 20% and a true rate of subjects seroconverting for SARS-CoV-2 S protein antibodies of 97.5%, the 2 conditions are met with a probability of 68% and 100% sample sizes of 150 and 1,200 respectively.

**Table 5 Probabilities (in %) for Assumed True Adverse Reaction Rates and for Assumed True Rates of Subjects with Seroconverting for SARS-CoV-2 S Protein Antibodies and Different Sample Sizes**

True adverse reaction rate (%)	Sample Size					
	150			1200		
	True rate of subjects with seroconverting for SARS-CoV-2 S protein antibodies (%)			True rate of subjects with seroconverting for SARS-CoV-2 S protein antibodies (%)		
	95	97.5	100	95	97.5	100
5	13	68	100	10	100	100
10	13	68	100	10	100	100
15	13	68	100	11	100	100
20	13	68	100	10	100	100
25	11	61	91	10	100	100
30	6	32	47	10	92	92
35	1	6	8	0	1	1

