### 10.3.5 Primary Analysis

#### 10.3.5.1 Primary Safety Analysis

The safety measurements will include:

2. AEs (type, intensity, frequency and relationship to trial vaccination), i.e., incidence and severity of AEs for both solicited local (injection site pain, redness, swelling, and itching) and solicited systemic events (fever, headache, fatigue, chills, myalgia, arthralgia, nausea/vomiting, and diarrhea) occurring on the day of vaccination and the following 7 days, and unsolicited events (occurring on the day of vaccination and the following 28 days).
3. SAEs and AESIs throughout the trial.

**Solicited AEs:** For reactogenicity assessment, the number and percentage of subjects with at least 1 solicited AE of any kind, by severity grade, for local, systemic, and overall, will be summarized after the first vaccination and after the second vaccination. For subjects with more than 1 episode of the same event, the maximum severity will be used for tabulations. In addition, the frequencies and severity of each solicited AE will be summarized for each vaccination day and the following 7 days. Similar tabulations will be

performed for solicited systemic AEs considered as related to the trial vaccine. The duration and severity of solicited AEs will be analyzed at subject level.

In addition, other indicators of safety (e.g., body temperature) will be collected and summarized. The number and percentage of subjects with Grade 3 adverse reaction(s) or SAEs considered as related to the trial vaccine according to the Investigator with the 95% CI based on the Beta (0.5, 0.5) prior distribution will be calculated and summarized.

**Unsolicited AEs:** Unsolicited AEs, SAEs and AESIs will be coded using the Medical Dictionary for Regulatory Activities (MedDRA) by System Organ Class (SOC) and Preferred Term (PT). The frequency and percentage of subjects reporting these events will be tabulated at the SOC and PT levels. Additional similar tabulations will be performed to evaluate severity and relationship to the trial vaccine. AEs that are reported as related to the trial vaccine will be considered trial vaccine-related; missing classifications concerning trial vaccine relationship will also be considered trial vaccine-related.

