8.3 Sample Size Considerations

The sample size of the trial ensures that sufficient safety and immunogenicity data will be available in a population with co-morbidities. The aim is to enroll 1,200 subjects. Due to the reasons described in section 6.1 and 6.2 the trial was stopped prior reaching the 1,200 subjects; hence 129 subjects were enrolled in total.

The trial is designed to provide a reasonable precision for an estimate of the number of subjects seroconverting for SARS-CoV-2 S protein RBD-specific antibodies and an acceptable rate of Grade 3 adverse reactions (defined as solicited local Grade 3 AEs, and solicited systemic or unsolicited Grade 3 AEs considered as related to the trial vaccine). Table 3 provides the estimate and 95% credibility interval for the observed numbers of subjects seroconverting for SARS-CoV-2 S protein antibodies for sample sizes of 150 (providing characteristics for a pre-defined co-morbidity) and 1,200 assuming a Beta (1.9, 0.1) priors

for seroconversion for SARS-CoV-2 S protein antibodies and Beta (0.5, 1.5) priors for Grade 3 adverse reactions are assumed.

Table 3 Estimate of Number of Subjects Seroconverting for SARS-CoV-2 S Protein Antibodies and 95% Credibility Interval (CI)

Rate (%)	Sample Size			
	150		1200	
	N	95% CI	N	95% CI
80	120	80.2 (73.5 - 86.1)	960	80 (77.7 - 82.2)
85	128	85.5 (79.5 - 90.6)	1020	85 (82.9 - 87)
90	135	90.1 (84.9 - 94.3)	1080	90 (88.3 - 91.6)
95	142	94.7 (90.6 - 97.6)	1140	95 (93.7 - 96.2)
100	150	99.9 (99.4 - 100)	1200	100 (99.9 - 100)

CI: credibility interval; N: subjects seroconverting for SARS-CoV-2 S protein antibodies

Table 4 below provides probabilities (in %) that the following 2 conditions are simultaneously met for assumed true adverse reaction rates and for assumed true rates of subjects seroconverting for SARS-CoV-2 S protein antibodies and for different sample sizes:

- There is a $\geq 80\%$ probability that the true rate of Grade 3 adverse reactions is $\leq 33\%$, and
- There is a $\geq 90\%$ probability that the true rate of subjects seroconverting for SARS-CoV-2 S protein antibodies is $> 95\%$.

For example, assuming a true adverse reaction rate of 20% and a true rate of subjects seroconverting for SARS-CoV-2 S protein antibodies of 97.5%, the 2 conditions are met with a probability of 68% and 100% sample sizes of 150 and 1,200 respectively.

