10.7.6 Grade 3 Adverse Reactions

Adverse reactions are defined as solicited local Grade 3 AEs, and solicited systemic or unsolicited Grade 3 AEs considered as related to the trial vaccine.

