12.7.1.2 Analysis of Solicited AEs

The following summaries of solicited AEs within 7 days after each trial vaccination and within 7 days after any trial vaccination will be provided. If not stated otherwise the maximum grade will be presented (grade 0 to grade 3).

- Summary of solicited AEs, local AEs and systemic AEs, overall and by maximum grade
- Summary of local AEs, overall and by maximum grade
- Summary of systemic AEs, overall and by maximum grade (occurrence of systemic AEs will also be presented from day -7 until day -1)*
- Summary of related systemic AEs, overall and by maximum grade*
- Duration (days) of solicited AEs, overall and for Grade 3 events
- Duration (days) of local AEs, overall and for Grade 3 events*
- Duration (days) of systemic AEs, overall and for Grade 3 events*
- Duration (days) of related systemic AEs, overall and for Grade 3 events*
- Daily summary of local AEs (only for each dose)*
- Daily summary of systemic AEs (only for each dose)*
- Daily summary of related systemic AEs (only for each dose)*
- Summary of time of onset (Day) for grade 3 solicited AEs, any solicited AEs, local, systemic AEs, and related systemic AEs*
- Time of onset (Day) of local AEs*
- Time of onset (Day) of systemic AEs*
- Time of onset (Day) of related systemic AEs*
- Individual grade 3 solicited local and systemic adverse events will be presented in a figure.*

In addition, number and percentage of subjects with solicited Grade 3 adverse reaction(s) or SAEs considered as related to the trial vaccine according to the Investigator with the 95% credibility interval based on the Beta (0.5, 1.5) prior distribution will be calculated and summarized. This analysis is not part of the abbreviated scope.

Solicited AEs occurring on the day of vaccination and the following 7 days will be listed separately as well.

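### SAP 6.4 drops the Grade 3 adverse-reaction rate because numbers are small, but for the overall analysis 129 subjects estimate it about as well as the 150 used to plan one co-morbidity

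*SAP*

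**What the plan says.** Protocol 10.3.5.1 plans to summarise "The number and percentage of subjects with Grade 3 adverse reaction(s) or SAEs considered as related to the trial vaccine", with a 95% credibility interval from a Beta(0.5, 0.5) prior. SAP 12.7.1.2 carries the analysis with a Beta(0.5, 1.5) prior, then says it is outside the abbreviated scope. SAP 6.4 gives the reason: the analysis with that "prior distribution and estimate will not be performed due to the small number of subjects". Appendix 4 lists no such table.

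SAP 10.7.6 defines the measure: "Adverse reactions are defined as solicited local Grade 3 AEs, and solicited systemic or unsolicited Grade 3 AEs considered as related to the trial vaccine". It is also the safety measure in the sample-size section (protocol 10.1, SAP 8.3). Those sections tabulate the probability "that the following 2 conditions are simultaneously met for assumed true adverse reaction rates" and assumed seroconversion rates. The first condition is at least 80% posterior probability that the Grade 3 adverse-reaction rate is at most 33%. The second is at least 90% "probability that the true rate of subjects seroconverting for SARS-CoV-2 S protein antibodies is" above 95%. The table covers n=150, described as characterising one co-morbidity, and n=1,200, the whole trial. SAP 6.3 and 8.3 put actual enrolment at 129.

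SAP 12.7.2 keeps the Beta-prior estimate and credibility interval for seroconversion in the per-protocol immunogenicity subset.

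**The concern.** Safety and reactogenicity is the first primary objective, and the Grade 3 adverse-reaction rate is the safety quantity used in the sample-size section. Dropping it leaves the report without an estimate or interval for that quantity, although the data are collected and SAP 10.7.9 already gives the formula.

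The stated reason is also applied unevenly. It removes a binomial estimate in the Safety Analysis Set but leaves the same kind of estimate for seroconversion in a population that needs both doses, compliance with the windows and a post-dose-2 sample. For neutralizing antibodies only a subset is tested.

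The tables that remain do not supply the missing figure. The 10.7.6 composite counts each subject once across three components, and one of these, solicited systemic events, counts only if related. In SAP 12.7.1.2 the "Summary of related systemic AEs, overall and by maximum grade" is starred, so it is out of scope. Grade 3 related unsolicited AEs and related SAEs are separate rows of the overall summary, and a subject may appear in several rows.

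SAP 12.7.1.2 also limits the composite to *solicited* Grade 3 reactions. SAP 10.7.6, SAP 6.4 and protocol 10.3.5.1 do not.

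**Working it through.** **Inputs.** Safety condition: posterior P(rate ≤ 33%) ≥ 80%, prior Beta(0.5, 1.5) (protocol 10.1, SAP 8.3). Seroconversion condition: posterior P(rate > 95%) ≥ 90%, prior Beta(1.9, 0.1) (same sections). Planning sizes 150 and 1,200; actual n=129 (SAP 6.3, 8.3).

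**Method.** The safety cut-off k is the largest count with BetaCDF(0.33; k + 0.5, n − k + 1.5) ≥ 0.80. The probability of meeting the condition at true rate p is BinomCDF(k; n, p). The seroconversion cut-off s is the smallest count with 1 − BetaCDF(0.95; s + 1.9, n − s + 0.1) ≥ 0.90. The joint probability is the product, taking the two outcomes as independent.

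**Reproducing the plan.** At n=150, k=44 and s=146. In the 100% seroconversion column, where only the safety condition matters, the results are 99.8, 90.5, 46.9 and 8.4% at true rates of 20, 25, 30 and 35%; SAP Table 4 prints 100, 91, 47 and 8. The worked example (20% reactions, 97.5% seroconversion) gives 0.998 × 0.678 = 67.7%, printed as 68%. At n=1,200, k=382, giving 92.1% at a true 30% and 1.1% at 35%, printed as 92 and 1.

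**Safety condition at the actual size.** At n=129, k=38 (29.5%): the posterior probability is 0.819 with 38 reactors and 0.765 with 39.

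| True rate | n=129 | n=150 | n=1,200 |
|---|---|---|---|
| 20% | 99.6% | 99.8% | 100% |
| 25% | 89.7% | 90.5% | 100% |
| 30% | 49.0% | 46.9% | 92.1% |
| 35% | 10.9% | 8.4% | 1.1% |

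At 5, 10 and 15% all three sizes give 100%. The largest gap between 129 and 150 is 10.9 − 8.4 = 2.5 points.

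**Interval width.** With 26 reactors of 129 (20.2%) the 95% credibility interval is 13.8 to 27.5%. With 30 of 150 (20.0%) it is 14.1 to 26.8%. With 13 of 129 (10.1%) it is 5.7 to 16.0%.

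**Sensitivity.**
- Smaller safety set (assumption: 100 subjects): k=29; the condition is met with probability 98.9% at a true 20% and 85.0% at 25%.
- Prior Beta(0.5, 0.5), as in protocol 10.3.5.1: k is unchanged at n=100, 129 and 150.
- Per co-morbidity (assumption: 129/7, about 18 each; actual counts are not given and strata overlap): k=4; 71.6% at a true 20% and 51.9% at 25%.
- Joint criterion, worked example at n=129: s=126, and 0.996 × 0.596 = 59.4%, against 67.7% at n=150. The seroconversion factor accounts for almost all of the fall (67.8% to 59.6%).

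**What the retained tables give.** The number of subjects with any Grade 3 solicited AE (Table 14.3.2.2.1) plus the number with a Grade 3 related unsolicited AE (Table 14.3.2.1.1) is an upper bound on the 10.7.6 count. It is not the count itself: it includes unrelated systemic events and counts some subjects twice.

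**The case against.** The planned trial was 1,200, not 150. Against 1,200, the probability of meeting the safety condition at a true 30% falls from 92% to 49%, and the objectives are also to be analysed per co-morbidity, where strata of about 18 say little. Both points stand. The comparison with 150 shows only that the whole of this trial is about as informative as one planned stratum, a size the documents themselves treat as worth characterising. The per-stratum weakness supports leaving out intervals by co-morbidity, not leaving out the overall figure.

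A reader might infer that the trial abandoned its one acceptance test for safety, or that the report cannot say anything about the 33% threshold. The documents support neither. The 33% condition is one half of a joint criterion that appears only in the sample-size sections. The analysis sections plan a count, a percentage and an interval, with no comparison to 33%, and SAP 12.0 limits the trial to descriptive statistics. The dropped composite also adds related SAEs, so it is not exactly the quantity in the 33% condition. And if the upper bound from the retained tables were 38 or fewer of 129, it would already show the condition met.

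The change is also disclosed, the composite is not among the listed primary safety endpoints, and the solicited and unsolicited tables, a Grade 3 figure and the listings remain. This lowers the weight of the point but does not rescue the stated reason.

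**Conclusion.** The point holds for the overall Safety Analysis Set. Small numbers do not justify dropping the overall Grade 3 adverse-reaction estimate: at n=129 the safety condition performs within 2.5 points of n=150 at every tabulated rate, and an observed 20% would carry an interval of about 14 to 28%. The SAP's retention of the matching seroconversion interval contradicts the reason given. The point does not extend to intervals by co-morbidity, and it does not make n=129 equivalent to the planned 1,200.

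The figures assume that all 129 enrolled subjects are in the safety set; with 100 the conclusion is the same. The choice between the two documented priors does not alter the cut-offs. What is lost is a direct estimate of the safety quantity used in sizing the trial, for which the retained outputs offer only an upper bound or hand-counting from listings.

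**What to change.** 1. In SAP 6.4, 12.7.1.2 and Appendix 4, reinstate one table for the overall Safety Analysis Set. It should show the number, percentage, estimate and 95% credibility interval (formula in 10.7.9) of subjects with at least one Grade 3 adverse reaction as defined in 10.7.6, and the same for that composite or a related SAE. Give counts only by co-morbidity.
2. In SAP 12.7.1.2, delete *solicited* before the Grade 3 adverse reactions, to match 10.7.6, 6.4 and protocol 10.3.5.1.
3. State that Beta(0.5, 1.5), the design prior, replaces the Beta(0.5, 0.5) in protocol 10.3.5.1.
4. Optionally, report the posterior probability that the 10.7.6 rate is at most 33%, labelled descriptive, since no decision rule is planned on it.

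The cost is the programming of one table from data already collected.

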## Description of changes to Trial CV-NCOV-003, Protocol Version 2.0

Subjects who already received at least 1 CVnCoV dose are requested to remain in the study for 3 months following their last CVnCoV dose for safety and immunogenicity follow-up. Subjects will follow the amended Schedule of Activities (Table 2) until they reach 3 months of follow-up post-CVnCoV last dose. The follow-up period including Visit 9/Day 211 and Phone Contact/Day 302 is removed. The previous End of Trial Visit/Day 393 is amended to 3 months post last injection of CVnCoV as described in Table 1.

Any subjects currently in screening will be considered screen failures and will not receive CVnCoV vaccination in line with the enrolment halt. No additional screenings will be performed.

Subjects will be provided with adequate information about the changes to the study, in accordance with applicable local regulations and in line with protocol section 12.4 “Informed Consent”.

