- Vital signs will be measured pre- and post-vaccination prior to discharge. Subjects will be observed for 1 hour following each vaccination. Vital signs must be within normal or clinically non-relevant abnormal ranges or have returned to pre-vaccination values for the subject to be discharged.
- Solicited and unsolicited AEs will be recorded in diaries. Diaries will be dispensed at Visit 1, Visit 2 and Visit 4.
- Subjects should complete the diary card for solicited systemic AEs as well as unsolicited AEs on a daily basis as of Day -7 (i.e., during 1 week before the first vaccination) to give an indication of their normal life with co-morbidities.

- i. SAEs, AESIs (including COVID-19), intercurrent medical conditions that may affect the immune response to vaccination, and AEs leading to vaccine withdrawal or trial discontinuation will be collected throughout the trial.
- j. Immunosuppressants or other immune-modifying drugs, with the exception of topically-applied, inhaled, or intranasal steroids, taken within 6 months prior to enrollment and any other medication/vaccination taken within 1 month prior to enrollment should be recorded to establish eligibility and any exception if relevant.
- k. Safety laboratory testing will be performed in the first 50 subjects enrolled and vaccinated from each co-morbidity. See Appendix 3 for an overview of the safety laboratory assessments.
- l. At Visit 6 and Visit 8 the safety laboratory only needs to be done if the previous result was abnormal.
- m. A blood sample for serum pregnancy testing will be taken from women of childbearing potential at screening to establish eligibility. Urine pregnancy tests will be performed before each vaccination, unless the serum pregnancy test was performed less than 3 days before and yielded a negative result.
- n. Swabs for COVID-19 testing will be collected in case the subject displays symptoms of acute respiratory infection (including, but not limited to COVID-19) (see Section 9.3).
- o. Blood samples on Day 1 and Day 29 must be collected prior to vaccination.
- p. This will include 12 subjects for each co-morbidity condition enrolled as part of the first 25 cases and 13 subjects enrolled as part of the next 25 subjects for each co-morbidity.
- q. In case a subject cannot come to site on the day after the vaccination due to vaccination reactions/side effects it is acceptable to conduct this visit within a window of +2 days.

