## 5.2 Stopping/Pausing Rules for Safety

### 5.2.1 Individual Subject Stopping Rules

Individual stopping AE rules will be applicable during the entire trial to ensure safe administration of the second dose to subjects vaccinated with the first vaccine dose.

Individual subject stopping rules are met in case any of the following events occur on the day of vaccination or the following 7 days (Days 1-8):

- An allergic/anaphylactic reaction considered as related to the trial vaccine.
- Any SAE considered as related to the trial vaccine.
- Any Grade 3 AE considered as related to the trial vaccine, with the following exceptions:
  - Transient Grade 3 systemic AE (fever, headache, fatigue, chills, myalgia, arthralgia, nausea/vomiting and diarrhea) considered as related to the trial vaccine that resolved within 24 hours to Grade ≤2
  - Transient Grade 3 local AE that resolved within 24 hours to Grade ≤2.

If any of these rules are met, the subject must not receive the second vaccine dose. The subject will be encouraged to continue participation until the end of the trial for safety and immunogenicity assessments.

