- g) Safety laboratory testing will be performed in the subjects who were allocated to this assessment at the time of enrolment. See Appendix 3 of Protocol version 2.0 for an overview of the safety laboratory assessments.
- h) On Day 43 and Day 120, the safety laboratory only needs to be done if the previous result was abnormal.
- i) Swabs for COVID-19 testing will be collected in case the subject displays symptoms of acute respiratory infection (including, but not limited to COVID-19) (see Section 9.3 of Protocol version 2.0).
- j) No blood draws for immunogenicity will be performed after the subject receives their first dose of authorised vaccine.

Sites shall continue to collect blood for this immunogenicity testing from the subjects who were allocated to this assessment at the time of enrolment.

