7.2 Secondary Objective

- To evaluate the humoral immune responses after 1 and 2 dose administrations of CVnCoV at different time points during the trial.

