
On Day 29, Day 120, Day 211 and Day 393:
 
The proportion of subjects seroconverting for
	
In subjects who received at least 1 dose of CVnCoV vaccine and for whom the baseline blood sample and at least 1 additional blood sample are available for analysis. Subjects receiving an authorized/licensed COVID-19 vaccine during the course of the trial will be censored at the day after intake. The secondary immunogenicity will be analyzed with the immunogenicity set. Day 211 and Day 393 will not be measured.

ENDPOINTS (subject level)	ESTIMANDS (population level)

SARS-CoV-2 S protein RBD antibodies, as measured by an immunoassay.
 
Individual SARS-CoV-2 S protein RBD-specific antibody levels in serum, as measured by an immunoassay.
 
GMTs of serum SARS-CoV-2 S protein RBD antibodies, as measured by an immunoassay.
 
In a subset of subjects*, on Day 29 and Day 120:
 
The proportion of subjects seroconverting for SARS-CoV-2 neutralizing antibodies, as measured by an activity assay.
 
Individual SARS-CoV-2 neutralizing antibody levels in serum, as measured by an activity assay.
 
GMTs of serum SARS-CoV-2 neutralizing antibodies, as measured by an activity assay.
	
Estimate of subjects seroconverted (SARS-CoV-2 spike protein-specific antibodies) with 95% credibility interval using prior beta(1.9, 0.1)
 
Number and percentage with exact 95% confidence intervals of subjects for who a seroconversion is observed (SARS-CoV-2 spike protein-specific antibodies)
 
Geometric mean of Fold Change from baseline with 95% CI of SARS-CoV-2 spike protein antibodies
 
Estimate of subjects seroconverted (SARS-CoV-2 neutralizing antibody levels in serum) with 95% credibility interval using prior beta(1.9, 0.1)
 
Number and percentage with exact 95% confidence intervals of subjects for who a seroconversion is observed (SARS-CoV-2 neutralizing antibody levels in serum)
 
Geometric mean of Fold Change from baseline with 95% CI of SARS-CoV-2 neutralizing antibody levels in serum

Exploratory	

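### The after-dose-1 (Day 29) antibody response is tabulated only in the two-dose per-protocol set, and the asymptomatic infection table uses that set with no declared change

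*SAP*

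**What the plan says.** **Timing.** Protocol Table 1 (footnotes) states: "Blood samples on Day 1 and Day 29 must be collected prior to vaccination". Day 29 is the day of dose 2.

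**Objective.** SAP 7.2 keeps the secondary objective: "To evaluate the humoral immune responses after 1 and 2 dose administrations of CVnCoV at different time points during the trial".

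**Analysis sets.** The Immunogenicity Set (SAP 9.5.1) needs one dose, a baseline sample and one later sample. The PPI (SAP 9.5.2) needs both doses in window, a sample from 14 days after dose 2, no important deviation affecting immunogenicity, and no interfering treatment.

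**Set used for antibodies.** The SAP 9.4 cell for the secondary endpoints reads "The secondary immunogenicity will be analyzed with the immunogenicity set. Day 211 and Day 393 will not be measured". SAP 6.4 replaces this: "the analysis will be performed with per protocol immunogenicity set for all available time points (Day 1(baseline), Day 29, Day 43 and Day 120"). SAP 12.7.2 presents Days 29 and 120 on the PPI and drops analyses on the Immunogenicity Set. Every antibody table and figure in Appendix 4 is titled PPI. The Immunogenicity Set remains only in listings (16.2.6.2 for RBD, 16.2.6.4 for neutralizing titers).

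**One-dose subjects are foreseen.** Protocol 5.2.1 bars dose 2 after a related allergic reaction, a related SAE or most related Grade 3 events, and adds: "The subject will be encouraged to continue participation until the end of the trial for safety and immunogenicity assessments". Amendment #1 asks anyone with at least one dose to stay "for 3 months following their last CVnCoV dose for safety and immunogenicity follow-up". Its Table 1 has a row for subjects whose last injection was on Day 1.

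**Asymptomatic infection.** SAP 9.4 and Listing 16.2.6.8 use the Immunogenicity Set. Table 14.2.6.1 in Appendix 4 uses the PPI. SAP 6.4 declares no change of set for this endpoint, and 12.7.3 names none.

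**The concern.** A Day 29 result answers a question about dose 1. Restricting it to subjects who went on to receive dose 2 on time and gave a sample from Day 43 on conditions the answer on events that happened after that dose. Some of those events may be consequences of dose 1: a subject stopped under 5.2.1 for a vaccine reaction is excluded because of how they responded to it. If such subjects differ in antibody response, the tabulated dose 1 result describes those who tolerated dose 1 and completed the course, not everyone given a first dose. Results are also presented by co-morbidity, where a few subjects can matter.

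For asymptomatic infection the stake is simpler: the table and its listing can cover different subjects, and a reader cannot tell which set was intended.

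**Working it through.** The plan states no figure for the Day 29 response, for the number of one-dose subjects or for the size of the PPI. There is nothing to reproduce, so the check compares the texts and then bounds the effect.

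**Step 1: who has a Day 29 result but is not in the PPI.** The amended Schedule of Activities plans RBD sampling at Day 29, and neutralizing sampling for the allocated subset. Only the Day 30 visit is limited to subjects who received dose 2, so the Day 29 draw is scheduled for one-dose subjects too. With a baseline and a Day 29 sample they enter the Immunogenicity Set. They cannot enter the PPI. Nor can two-dose subjects dosed out of window or without a sample from Day 43 on.

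**Step 2: formula.** Let n be the subjects in the PPI and k the omitted subjects with a Day 29 result. Then

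PPI rate − full-set rate = [k/(n+k)] × (PPI rate − rate in the omitted).

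The last factor lies between −1 and 1, so each omitted subject contributes at most 1/(n+k).

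**Step 3: bound per omitted subject, RBD seroconversion.**
- Overall, if all 129 enrolled (SAP 6.3) have Day 1 and Day 29 samples: 1/129 = 0.78 points.
- Per co-morbidity: an even split would give 129/7 = 18.4 subjects, though subjects with several conditions count in each stratum. For assumed strata of 10, 18 and 30: 1/10 = 10.0, 1/18 = 5.6 and 1/30 = 3.3 points.

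The 1/129 bound does not carry over to the neutralizing assay, which is run in a subset of about 25 per co-morbidity. In a full subset of 25 it is 1/25 = 4.0 points per omitted subject within that co-morbidity, and more if the subset was not filled.

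**Step 4: illustrations (k and the rate differences are assumptions).**

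| Omitted k of 129 | Shift if rates differ by 10 points | Shift if they differ by 30 points |
|---|---|---|
| 6 | 6/129 × 10 = 0.5 | 1.4 |
| 26 | 26/129 × 10 = 2.0 | 6.0 |
| 52 | 52/129 × 10 = 4.0 | 12.1 |

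If the omitted respond alike, the shift is zero. The formula is symmetric, and the documents do not indicate a direction.

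**Step 5: precision.** Exact (Clopper-Pearson) 95% intervals at about 95%, a scenario borrowed from the sample-size table and not a Day 29 assumption of the plan:
- 123/129: 90.2 to 98.3 (8.1 points)
- 103 subjects, 98 responding: 89.0 to 98.4 (9.4)
- 90 subjects, 86 responding: 89.0 to 98.8 (9.8)

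At an assumed 70%, the interval is 61.1 to 77.5 with 129 subjects and 60.1 to 78.5 with 103. The loss of precision is small.

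**Step 6: Table 14.2.6.1.** Anti-N blood is not drawn at Day 29. A one-dose subject can therefore add Day 1 and Day 43 to this table, but not Day 120, because their follow-up ends at Day 91. Two-dose subjects outside the PPI could add all three days. The mismatch is real but narrow.

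**The case against.** The strongest reply is that the PPI is what the protocol intends. Protocol 10.2 and SAP 9.5.2 name it the primary population for both antibody responses, without limiting that to Day 43, and one fixed cohort across Days 1, 29, 43 and 120 is a sound longitudinal display. The switch is stated openly in 6.4, whose first bullet frames it as a reduced scope for a reduced sample, although no reason is attached to the change of set itself. This stands, and it is why the PPI display should stay. It does not make the PPI the right set for a result that precedes dose 2.

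A reader might infer that the SAP contradicts itself, since 9.4 still names the Immunogenicity Set and 12.7.2 first drops analyses on it and then plans figures for it. The documents largely settle this. SAP 6.3 keeps superseded text by design ("The original planned analysis, definition and scope of outputs will remain in the version 2.0 of SAP") and points to Appendix 4 for the planned outputs, and the lead-ins of 9.4 and 12.7 defer to the same places. What remains is wording.

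A third reply is that a Day 29 sample in one-dose subjects is not assured. Protocol section 8 leaves immunogenicity blood to the Investigator's discretion once vaccination is discontinued, and under the amendment "No blood draws for immunogenicity will be performed after the subject receives their first dose of authorised vaccine". This also stands: it may shrink the omitted group, possibly to nobody. Finally, subjects who missed dose 2 only because of the programme-level pause give no evident reason for a different Day 29 response.

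**Conclusion.** The point holds as a minor one. The dose 1 objective in SAP 7.2 is tabulated only in subjects selected by later events. Any other subject with a Day 29 result is visible only in listings.

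The size cannot be known from the documents and may be zero. The bound of 0.8 points per omitted subject overall assumes that all 129 have both samples and applies to RBD seroconversion only; the stratum bounds rest on assumed stratum sizes. The analysis is descriptive and no individual value is lost. A reader might go further and infer that the Day 29 rate is biased upward, or that the primary result is compromised. Neither is supported: no count, rate or direction is given for the omitted subjects, and the Day 43 analysis, which by its objective concerns two doses, properly uses the PPI.

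The set for Table 14.2.6.1 is a separate, small inconsistency that no declared change covers.

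**What to change.** - Keep the PPI for Day 43 and for the longitudinal display.
- Add Day 29 results on the Immunogenicity Set for Tables 14.2.1.1, 14.2.2.1 and 14.2.3.1. Table 14.2.4.1 is limited to Day 43 and needs no change. Footnote that this set readmits subjects with important deviations or interfering treatments. The censoring rule in SAP 10.9 still applies after an authorised vaccine.
- Run Table 14.2.6.1 on the Immunogenicity Set, to match SAP 9.4 and Listing 16.2.6.8.
- Housekeeping: align the wording of 9.4, 12.7.2 and 12.7.3 with 6.4. This includes whether the COVID-19 endpoints are kept, since 6.4 drops the confirmed-case analysis while 12.7.3 retains both exploratory endpoints.

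The cost is a few extra tables in an abbreviated report, run with existing programs on a set already defined. No new data are needed. Subjects with no sample after baseline stay outside the Immunogenicity Set, so nothing is recovered for them. If nobody with a Day 29 sample falls outside the PPI, the two displays will agree and the question is closed.
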